6.0 CLINICAL TRIAL PROCESSES AND PROCEDURES

The schedule of study visits, procedures, and assessments are in Section 7.0. Individual trial procedures are described in detail below.

6.1 STUDY SITE

Patients will be evaluated and treated at the University of Pittsburgh Medical Center (UPMC) and the Outpatient Services of the UPMC Hillman Cancer Center. Patients will be registered and data management will be performed by Clinical Research Services of the UPMC Hillman Cancer Center.

6.2 PROCEDURE FOR REGISTRATION AND RANDOMIZATION (IF APPLICABLE) OF SUBJECTS

Patients must not start protocol treatment prior to registration. Subjects can be enrolled after eligibility criteria are met. Registration will require the following information: 1) protocol name and number; 2) date treatment begins; 3) subject name; 4) date of birth; 5) primary study physician; 6) confirmation of eligibility; 7) copies of the informed consent signature page; 98) verification that the informed consent was signed. If a patient will be randomized to treatment (when the difference between OmniSeq LAG3 and CTLA4 scores are less than 15.2), they will be randomized 1:1 to anti-LAG3 or anti-CTLA4. Treatment will be block-randomized, with blocks of size 4.

Randomization will be performed via the UPMC Hillman Cancer Center Biostatistics Facility randomization system (<https://randomize.upci.pitt.edu/randomizer/home.seam>). A standard operating procedure will describe the use of the system.

6.3 INFORMED CONSENT

The study team must obtain documented consent from each potential subject prior to participating in a clinical trial. Consent must be documented by the subject's dated signature. A copy of the signed, dated and timed consent form should be given to the subject before participation in the trial. The initial informed consent form, any subsequent revised written informed consent form and any written information provided to the subject must receive the Institutional Review Board's (IRB's) approval/favorable opinion in advance of use. The subject should be informed in a timely manner if new information becomes available that may be relevant to the subject's willingness to continue participation in the trial. The communication of this information will be provided and documented via a revised consent form or addendum to the original consent form that captures the subject's dated signature.

6.4 CONCOMITANT MEDICATIONS (allowed and prohibited)

Concomitant medications specifically prohibited in the exclusion criteria are not allowed during the ongoing trial. If there is a clinical indication for one of these or other medications specifically prohibited during the trial, discontinuation from trial therapy may be required. The final decision on any supportive therapy rests with the investigator and/or the subject's primary physician.

6.4.1 ACCEPTABLE CONCOMITANT MEDICATIONS

All treatments that the investigator considers necessary for a subject's welfare may be administered at the discretion of the investigator in keeping with the community standards of medical care. All concomitant medication will be recorded on the research record including all prescription, over-the-counter (OTC), herbal supplement, and IV medications. If changes occur during the trial period, documentation of drug dosage, frequency, route, and date may also be included research record.

All concomitant medications received within 30 days before the first dose of trial treatment and 30 days after the last dose of trial treatment should be recorded. Concomitant medications administered after 30 days after the last dose of trial treatment should be recorded for SAEs.

6.4.2. PROHIBITED CONCOMITANT MEDICATIONS

Subjects are prohibited from receiving the following therapies during the Screening and Treatment Phase (including retreatment for post-complete response relapse) of this trial:

1. Anti-cancer systemic chemotherapy or biological therapy
2. Immunotherapy not specified in this protocol
3. Glucocorticoids at a dosage of $\geq 10\text{mg}$ of prednisone or equivalent for any purpose other than the treatment or prophylaxis of any adverse event (intermittent use of bronchodilators or local steroid injections is allowed),

Subjects who, in the assessment by the investigator, require the use of any of the aforementioned treatments for clinical management should be removed from the trial. Subjects may receive other medications that the investigator deems to be medically necessary.

The Exclusion Criteria describes other medications which are prohibited in this trial.

6.4.3 DIET

Subjects should maintain a normal diet unless modifications are required to manage an AEs such as diarrhea, nausea or vomiting, mucositis, or dysphagia. Consultation with nutrition during radiation therapy is strongly recommended.

6.4.4 PREGNANCY TEST AND CONTRACEPTION:

6.4.4.1 CONTRACEPTION GUIDANCE FOR FEMALE PARTICIPANTS OF CHILD BEARING POTENTIAL

One of the highly effective methods of contraception listed below is required during study duration and until the end of relevant systemic exposure, defined as 24 weeks after the end of study treatment.*

Highly Effective Contraceptive Methods That Are User Dependent

Failure rate of <1% per year when used consistently and correctly.^a

- Combined (estrogen- and progestogen-containing) hormonal contraception associated with inhibition of ovulation^b
 - oral
 - intravaginal
 - transdermal
- Progestogen-only hormonal contraception associated with inhibition of ovulation
 - oral
 - injectable

Highly Effective Methods That Are User Independent

- Implantable progestogen-only hormonal contraception associated with inhibition of ovulation ^b
- Hormonal methods of contraception including oral contraceptive pills containing a combination of estrogen and progestrone, vaginal ring, injectables, implants and intrauterine hormone-releasing system (IUS)^c
- Intrauterine device (IUD)^c
- Bilateral tubal occlusion
- Vasectomized partner
A vasectomized partner is a highly effective contraception method provided that the partner is the sole male sexual partner of the WOCBP and the absence of sperm has been confirmed. If not, an additional highly effective method of contraception should be used.
- Sexual abstinence
Sexual abstinence is considered a highly effective method only if defined as refraining from heterosexual intercourse during the entire period of risk associated with the study drug. The reliability of sexual abstinence needs to be evaluated in relation to the duration of the study and the preferred and usual lifestyle of the participant.
- It is not necessary to use any other method of contraception when complete abstinence is elected.
- WOCBP participants who choose complete abstinence must continue to have pregnancy tests, as specified in Section 2.
- Acceptable alternate methods of highly effective contraception must be discussed in the event that the WOCBP participants chooses to forego complete abstinence

NOTES:

^a Typical use failure rates may differ from those when used consistently and correctly. Use should be consistent with local regulations regarding the use of contraceptive methods for participants participating in clinical studies.

^b Hormonal contraception may be susceptible to interaction with the study drug, which may reduce the efficacy of the contraceptive method. Hormonal contraception is permissible only when there is sufficient evidence that the IMP and other study medications will not alter hormonal exposures such that contraception would be ineffective or result in increased exposures that could be potentially hazardous. In this case, alternative methods of contraception should be utilized.

^c Intrauterine devices and intrauterine hormone releasing systems are acceptable methods of contraception in the absence of definitive drug interaction studies when hormone exposures from intrauterine devices do not alter contraception effectiveness

Unacceptable Methods of Contraception*

- Male or female condom with or without spermicide. Male and female condoms cannot be used simultaneously
- Diaphragm with spermicide
- Cervical cap with spermicide
- Vaginal Sponge with spermicide
- Progestogen-only oral hormonal contraception, where inhibition of ovulation is not the primary mechanism of action
- Periodic abstinence (calendar, symptothermal, post-ovulation methods)
- Withdrawal (coitus interruptus)
- Spermicide only
- Lactation amenorrhea method (LAM)

* Local laws and regulations may require use of alternative and/or additional contraception methods.

6.4.4.2 CONTRACEPTION GUIDANCE FOR MALE PARTICIPANTS WITH PARTNER(S) OF CHILD BEARING POTENTIAL.

Male participants with female partners of childbearing potential are eligible to participate if they agree to the following during the treatment and until the end of relevant systemic exposure.

- Inform any and all partner(s) of their participation in a clinical drug study and the need to comply with contraception instructions as directed by the investigator.
- Male participants are required to use a condom for study duration and until end of relevant systemic exposure defined as 33 weeks after the end of study treatment.
- Female partners of males participating in the study to consider use of effective methods of contraception until the end of relevant systemic exposure, defined as 7 months after the end of treatment in the male participant.
- Male participants with a pregnant or breastfeeding partner must agree to remain abstinent from penile vaginal intercourse or use a male condom during each episode of penile penetration during the treatment and until 33 weeks after the end of study treatment.
- Refrain from donating sperm for the duration of the study treatment and until 7 months after the end of study treatment.

6.5 USE IN PREGNANCY

If a subject inadvertently becomes pregnant while on study treatment, the subject will immediately be removed from the study. The site will contact the subject at least monthly and document the subject's status until the pregnancy has been completed or terminated. The outcome of the pregnancy will be reported to the sponsor and to BMS as per section 9.3. The study investigator will make every effort to obtain permission to follow the outcome of the pregnancy and report the information to the sponsor and to BMS. If a male subject impregnates his female partner, the study personnel at the site must be informed immediately, and the pregnancy must be reported to the sponsor and to BMS, and followed as described above.

6.6 USE IN NURSING WOMEN

It is unknown whether nivolumab, relatlimab or ipilimumab is excreted in human milk. Since many drugs are excreted in human milk, and because of the potential for serious adverse reactions in the nursing infant, subjects who are breast-feeding are not eligible for enrollment.

6.7 SUBJECT WITHDRAWAL/DISCONTINUATION CRITERIA

Subjects may withdraw consent at any time for any reason or be dropped from the trial at the discretion of the

investigator should any untoward effect occur. In addition, a subject may be withdrawn by the Investigator if enrollment into the trial is inappropriate, the trial plan is violated, or for administrative and/or other safety reasons.

A subject must be discontinued from the trial treatment for any of the following reasons:

- The subject withdraws consent.
- Confirmed radiographic disease progression. See Section 13.0
- Unacceptable adverse events as described in Section 12.0
- Intercurrent illness that prevents further administration of treatment
- Investigator's decision to withdraw the subject
- The subject has a confirmed positive serum pregnancy test
- Noncompliance with trial treatment or procedure requirements
- The subject is lost to follow-up
- Administrative reasons

6.8 SUBJECT REPLACEMENT STRATEGY

A subject who withdraws from the trial for reasons other than toxicity, progression of disease or death and withdraws before the initial efficacy evaluation can be replaced. These cases will be recorded and accounted for in the report of the trial.

6.9 Tumor Tissue Acquisition.

A Patient must provide adequate tumor tissue (minimum of 2 cores or a surgical/incisional/excisional biopsy) prior to starting study for analysis for gene expression of LAG3 and CTLA4 per OmniSeq Immune Report Card. FNA is not adequate. Archival tissue can only be used if it was obtained in the recurrent/metastatic setting and no subsequent treatment was received after biopsy. If this is not available a new biopsy is needed. If a patient undergoes a second biopsy on trial for potential retreatment (see section 7.4) a new biopsy of adequate tumor tissue (as defined above) will need to be obtained. Biopsy will be obtained including but not limited to: radiology guided, surgical procedure, during direct laryngoscopy. The investigator to should obtain adequate tumor tissue in the least invasive way possible to minimize risks to the patient as much as possible.

7.0 TRIAL TREATMENTS

7.1 STUDY CALENDAR (SCREENING)

Eligibility Assessments	Screening Day -28 to -1
Informed consent	X
Inclusion/Exclusion Criteria	X
Medical History	X
Medication History	X
Physical Examination	X
Vital Signs and Weight¹	X
ECOG PS	X
12 Lead EKG	X
Pregnancy Test-urine or serum B-HCG²	X
PT/INR and aPTT	X
CBC w/ differential³	X
Comprehensive Metabolic Panel⁴	X
TSH, FT4, T3	X
Hepatitis C Ab⁵	X
Hep B sAg, Hep B sAb	X
HIV 1/2 antibodies	X
Troponin⁶	X
2D echo/MUGA⁷	X
Tumor Tissue⁸	X
Tumor Imaging⁹	X

1. Vital signs to include temperature, pulse, respiratory rate, blood pressure. Height will be recorded at screening visit only.
2. For women of reproductive potential, a urine pregnancy test will be performed during screening. If a urine pregnancy result cannot be confirmed as negative, then a serum pregnancy test will be required. Pregnancy testing may be repeated if pregnancy is suspected. Repeat pregnancy testing must occur within 1 day prior to first dosage of study drugs.
3. CBC to include white blood cells, hgb/hct, platelets and differential.
4. Chemistry tests to include sodium, Potassium, Chloride, CO2, Glucose, BUN, Creatinine, Calcium, total Protein, Albumin, AST, ALT, Alkaline Phosphatase, Total Bilirubin, Magnesium, and Phosphorus
5. If Hep C Ab is positive a Hep C virus RNA PCR can be checked. If the Hep C virus RNA PCR is negative then the patient does not have active Hep C and therefore would still qualify for the trial.
6. Troponin T (TnT) or I (TnI) will be checked. If $> 2 \times$ institutional ULN patients will be excluded. Subjects with TnT or TnI levels between > 1 to $2 \times$ ULN will be permitted if repeat levels within 24 hours are $\leq 1 \times$ ULN. If TnT or TnI levels are > 1 to $2 \times$ ULN within 24 hours, the subject may undergo a cardiac evaluation and be considered for treatment based on the discretion of the PI. When repeat levels within 24 hours are not available, a repeat test should be conducted as soon as possible. If TnT or TnI repeat levels beyond 24 hours are $< 2 \times$ ULN, the subject may undergo a cardiac evaluation and be considered for treatment, based on the discretion of the PI.
7. Transthoracic 2D echo is required during screening to evaluate ejection fraction. TTE or MUGA (TTE preferred test) has to have been done within 6 months from first study drug administration.
8. Patient must provide adequate tumor tissue (core or surgical/incisional/excisional biopsy) prior to starting study for analysis for gene expression of LAG3 and CTLA4 per OmniSeq Immune Report Card. FNA is not adequate. Archival tissue can only be used if it was obtained in the recurrent/metastatic setting and no subsequent treatment was received after biopsy. If this is not available a new biopsy is needed. If a patient undergoes a second biopsy on trial for potential retreatment a new biopsy of adequate tumor tissue (as defined above) will need to be obtained.
9. Tumor imaging is required at baseline and then every 8 weeks (± 7 days) during study treatment. Unless there is a dose delay, imaging should be done within 7 days prior to odd cycles. If a patient completes 24 cycles without progression repeat imaging will be done every 3 months (± 7 days) from last receipt of study therapy as per section 7.7. Tumor imaging should be at minimum with a CT neck with IV contrast, CT chest with IV contrast, and CT abdomen/pelvis with IV contrast. If MRI is determined to be a better modality to follow the patients malignancy an MRI can be used. If a patient has an allergy to CT contrast dye that precludes usage than MRI can be used for disease in the head and neck and CT non-contrast can be used for the chest, abdomen and pelvis if the investigator has determined that tumor measurements can be made without the usage of CT IV contrast.

7.2 STUDY CALENDAR FOR PATIENTS TREATED WITH NIVOLUMAB AND RELATLIMAB (CYCLE = 28 DAY)

Assessments	C1D1	C1D14 (±3d)	C2D1 (± 3d)	C2D14 (±3d)	C3D1 and D1 of all subsequent cycles (± 3d)	Safety Follow up ^B	Survival Follow up ^C
Administer Nivolumab ^A	X		X		X		
Administer Relatlimab ^A	X		X		X		
Medical History	X		X		X	X	X
Medication History	X		X		X	X	
Physical examination	X	X	X	X	X	X	
Vital Signs and Weight ¹	X	X	X	X	X	X	
ECOG PS	X	X	X	X	X	X	
12 Lead EKG ²	X	X	X	X	X		
Review adverse events	X	X	X	X	X	X	
Pregnancy Test ³	X						
CBC w/ differential ^{4,5}	X	X	X	X	X	X	
Comprehensive Metabolic Panels ⁵	X	X	X	X	X	X	
TSH, FT4, T3 ⁶					X		
Troponin ^{2,7}	X	X	X	X	X		
Tumor Tissue ⁸							
Biomarker Studies/ Microbiome ⁹	X				X (Cycle 3 only)		
Tumor Imaging ¹⁰					X		

1. Vital signs to include temperature, pulse, respiratory rate, blood pressure. Height will be recorded at screening visit only.
2. For patients receiving Relatlimab, troponin and 12 lead EKG will be done every 2 weeks for the first 2 months. Subsequently they will be done at the discretion of the treating investigator. Troponin can be drawn within 48 hours of D1 of each cycle
3. For women of reproductive potential, a urine pregnancy test will be performed within 1 day prior to first dosage of study drugs. If a urine pregnancy result can't be confirmed as negative, then a serum pregnancy test will be required. Pregnancy testing may be repeated if pregnancy is suspected.
4. CBC to include white blood cells, hgb/hct, platelets and differential.
5. CBC and CMP will be done at scheduled visits every 2 weeks for the first 2 cycles and then prior each cycle of study drug therapy. These labs can be obtained up to 72 hours prior to study therapy. Chemistry tests to include sodium, Potassium, Chloride, CO2, Glucose, BUN, Creatinine, Calcium, total Protein, Albumin, AST, ALT, Alkaline Phosphatase, Total Bilirubin, Magnesium, and Phosphorus
6. Thyroid function tests (TSH, Free T4, Total T3) will be done prior to every 3rd cycle or more frequently at the discretion of the treating physician
7. Troponin T (TnT) or I (TnI) will be checked. If $> 2 \times$ institutional ULN patients will be excluded. Subjects with TnT or TnI levels between > 1 to $2 \times$ ULN will be permitted if repeat levels within 24 hours are $\leq 1 \times$ ULN. If TnT or TnI levels are > 1 to $2 \times$ ULN within 24 hours, the subject may undergo a cardiac evaluation and be considered for treatment based on the discretion of the PI. When repeat levels within 24 hours are not available, a repeat test should be conducted as soon as possible. If TnT or TnI repeat levels beyond 24 hours are $< 2 \times$ ULN, the subject may undergo a cardiac evaluation and be considered for treatment, based on the discretion of the PI.
8. If a patient undergoes a second biopsy on trial for potential retreatment a new biopsy (core or surgical/incisional/excisional) will need to be obtained. See section 7.6
9. Blood will be drawn for correlative studies. Instructions on tubes needed for biomarkers study blood draws are in section 14.0. They will be drawn prior to first dosage of study drug combination C1D1, and C3D1 prior to infusion, and at next study visit after progression is confirmed. Microbiome studies as per section 14.0 will also be obtained at these same timepoints.
10. Tumor imaging is required at baseline and then every 8 weeks (+/- 7 days) during study treatment. Unless there is a dose delay, imaging should be done within 7 days prior to odd cycles. If a patient completes 24 cycles without progression repeat imaging will be done every 3 months (+/- 7 days) from last receipt of study therapy as per section 7.7. Tumor imaging should be at minimum with a CT neck with IV contrast, CT chest with IV contrast, and CT abdomen/pelvis with IV contrast. If MRI is determined to be a better modality to follow the patients malignancy an MRI can be used. If a patient has an allergy to CT contrast dye that precludes usage than MRI can be used for disease in the head and neck and CT non-contrast can be used for the chest, abdomen and pelvis if the investigator has determined that tumor measurements can be made without the usage of CT IV contrast.

A See section 7.4 for details of treatment with Relatlimab plus Nivolumab

B For patients with progressive disease who don't qualify for a second treatment on study per section 7.6, or who are withdrawn from the study for any reason including toxicity, safety follow up will occur for patients that discontinue trial treatment for any reason 30 days (+/- 7 days) after the last dosage of study drug combination

C For patients with progressive disease who don't qualify for a second treatment on study per section 7.6, or who are withdrawn from the study for any reason including toxicity, survival follow up will occur starting 3 months after the last dosage of study drug. A call will be placed to the patient for survival status and if alive whether subsequent anti-neoplastic therapy was received. Patient will receive calls every 3 months for the first year and then every 6 months for the second year, then yearly thereafter.

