 - e. History of other clinically significant cardiovascular disease (i.e., cardiomyopathy, congestive heart failure with New York Heart Association [NYHA] functional classification III-IV, pericarditis, significant pericardial effusion, significant coronary stent occlusion, poorly controlled deep venous thrombosis, etc.);
 - f. Cardiovascular disease-related requirement for daily supplemental oxygen
 - g. History of two or more MIs OR two or more coronary revascularization procedures
 - h. Subjects with history of myocarditis, regardless of etiology.

9. A confirmed history of encephalitis, meningitis, or uncontrolled seizures in the year prior to informed consent
10. Subjects with history of life-threatening toxicity related to prior immune therapy (eg. anti-CTLA-4 or anti-PD-1/PD-L1 treatment or any other antibody or drug specifically targeting T-cell co-stimulation or immune checkpoint pathways) except those that are unlikely to re-occur with standard countermeasures (eg, hormone replacement after endocrinopathy).
11. Troponin T (TnT) or I (TnI) $> 2 \times$ institutional ULN. Subjects with TnT or TnI levels between > 1 to $2 \times$ ULN will be permitted if repeat levels within 24 hours are $\leq 1 \times$ ULN. If TnT or TnI levels are > 1 to $2 \times$ ULN within 24 hours, the subject may undergo a cardiac evaluation and be considered for treatment based on the discretion of the PI. When repeat levels within 24 hours are not available, a repeat test should be conducted as soon as possible. If TnT or TnI repeat levels beyond 24 hours are $< 2 \times$ ULN, the subject may undergo a cardiac evaluation and be considered for treatment, based on the discretion of the PI.
12. Has a history of non-infectious pneumonitis that required steroids, evidence of interstitial lung disease, or currently active non-infectious pneumonitis.
13. Has a history or current evidence of any condition, therapy, or laboratory abnormality that might confound the results of the trial, interfere with the subject's participation for the full duration of the trial, or is not in the best interest of the subject to participate, in the opinion of the treating investigator.
14. Has known psychiatric or substance abuse disorders that would interfere with cooperation with the requirements of the trial.

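### Footnote 7 of the Section 7.2 relatlimab calendar applies the screening troponin rule after dosing, where it conflicts with the mandatory hold in Section 12.2

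*Combined protocol and SAP*

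**What the plan says.** **Eligibility.** Exclusion criterion 11 (Section 5.2) sets a troponin limit for entry, with a conditional band: "institutional ULN. Subjects with TnT or TnI levels between > 1 to" 2 x ULN. Footnote 6 of the screening calendar (Section 7.1) restates it, beginning "Troponin T (TnT) or I (TnI) will be checked".

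**On treatment, calendar.** Footnote 7 of the relatlimab calendar (Section 7.2) repeats screening footnote 6 word for word. The troponin row carries footnotes 2 and 7 and is marked at C1D1, C1D14, C2D1, C2D14 and "C3D1 and D1 of all subsequent cycles". Nothing limits footnote 7 to C1D1 or points to Section 12.2. Above 2 x the limit, the text runs "institutional ULN patients will be excluded. Subjects with TnT or TnI levels between > 1 to" 2 x ULN are allowed if a repeat within 24 hours is normal. If the level is still in that band, "the subject may undergo a cardiac evaluation and be considered for treatment based on the discretion of the PI".

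**On treatment, dose delay.** Section 12.2, which covers both regimens, lists events for which study drugs have to be held. Its troponin line applies to all elevations: dosing is delayed for a prompt cardiac evaluation, and the PI then decides on further treatment. It gives no threshold and no exception for a normal repeat.

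**Discontinuation.** Section 12.3 lists Grade 3 or higher drug-related myocarditis but names no troponin level.

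**Timing.** Footnote 2 of Section 7.2 schedules troponin "every 2 weeks for the first 2 months. Subsequently they will be done at the discretion of the treating investigator", and adds "Troponin can be drawn within 48 hours of D1 of each cycle".

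**The concern.** A rule written to decide who may enter the trial also appears as the instruction for patients who have already had relatlimab. Before the first dose, a mildly raised troponin that normalises on repeat can reasonably be let through. After dosing, the same result may be an early sign of drug-related myocarditis, and Section 12.2 treats it that way.

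Section 2.5.5 reports Grade 5 myocarditis as one of two dose-limiting toxicities in 5 evaluable patients at 240 mg relatlimab with 240 mg nivolumab, which led to testing at 160 mg. Section 12.2 separately holds drug for myocarditis of any grade. The exposed situation is therefore a raised troponin before any diagnosis has been made, which is what scheduled troponin monitoring is meant to catch. Someone working from the calendar could dose after one normal repeat, or treat the evaluation as optional.

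**Working it through.** No sample size, error rate or stated figure is involved, so the check is a comparison of the two rules, band by band, for a relatlimab patient after the first dose.

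| Troponin result | Section 7.2, footnote 7 | Section 12.2 | Comparison |
|---|---|---|---|
| > 1 to 2 x ULN, repeat within 24 h at or below ULN | Allowed; no delay or evaluation required | Hold and evaluate | Footnote looser |
| > 1 to 2 x ULN, repeat still in band | Evaluation optional, then PI discretion; no hold stated | Hold and evaluate, then PI discretion | Footnote looser |
| > 1 to 2 x ULN, repeat only beyond 24 h and < 2 x ULN | Evaluation optional, then PI discretion | Hold and evaluate, then PI discretion | Footnote looser |
| > 2 x ULN | Excluded | Hold and evaluate, then PI discretion | Outcomes differ if exclusion means ending treatment; footnote then stricter |

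Two points of reading:

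- The last sentence of footnote 7 (a repeat beyond 24 hours and below 2 x ULN) follows "When repeat levels within 24 hours are not available, a repeat test should be conducted as soon as possible". That sentence in turn follows the > 1 to 2 x ULN rules, so it is unclear whether the last sentence also rescues a patient whose first value was above 2 x ULN.
- The Section 12.2 list is introduced as drug-related events, but its troponin line covers all elevations, and its purpose is evaluation before the cause is known. A narrow reading does not remove the mismatch.

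**Where footnote 7 applies.** With 28-day cycles, day 1 of cycle n is study day 28(n - 1) + 1. The marked draws through C3D1 are:

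- C1D1 = day 1
- C1D14 = day 14
- C2D1 = 28 + 1 = day 29
- C2D14 = 28 + 14 = day 42
- C3D1 = 56 + 1 = day 57

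That is 5 draws. One precedes the first dose, leaving 5 - 1 = 4 after it. Two of those (C2D1, C3D1) fall on infusion days; at C1D14 and C2D14 the conflict concerns the next scheduled dose. Beyond C3D1 the table keeps marking troponin while footnote 2 makes it discretionary, so no further count is used. These counts show which visits carry the wrong text. They do not show how often the two rules would give different answers, because that needs a raised value and the documents give no rate.

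**The case against.** The strongest reply is that a binding on-treatment rule already exists. Section 12.2 is mandatory, covers both regimens and allows no exception. Footnote 7 never tells anyone to dose without a delay; its language is permissive, so at > 1 to 2 x ULN a site that follows Section 12.2 satisfies both texts. This stands, and it limits the point to an inconsistency. A reader might infer that the protocol has no troponin rule after dosing, or that it directs treatment through an elevation. Section 12.2 contradicts both.

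Second, above 2 x ULN the word *excluded* is an eligibility term. If it cannot govern a patient already on treatment, Section 12.2 applies alone. This largely stands: the conflict in that band depends on reading the word as ending treatment, which no visible text says. A reader might also infer added cardiac risk in this band, but on that reading the footnote means less drug exposure, not more.

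Third, there are backstops. Section 12.3 item 3 stops treatment for Grade 4 drug-related laboratory abnormalities, and its exceptions do not name troponin. Sections 12.2 and 12.3 (item 5) also give the investigator judgment to delay or stop. Section 6.1 names a single centre, and this trial uses 160 mg relatlimab, below the dose level of the cited toxicities. All of this is correct and lowers the risk. None of it tells staff at a calendar visit that footnote 7 yields to Section 12.2.

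Finally, Appendix II contains a relatlimab myocarditis algorithm whose figure is not shown. It may address priority, so the statement here is confined to the visible text.

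**Conclusion.** Footnote 7 is wrong as written for every draw after the first dose: it is an internal inconsistency in a safety rule. At > 1 to 2 x ULN it is plainly looser than Section 12.2. Above 2 x ULN it is undefined for a patient on treatment and, on one reading, stricter. The mismatch is certain from the text. The consequence, dosing without the required hold, is possible rather than shown, and it assumes that staff act on the calendar without consulting Section 12.2.

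No frequency, patient count or statistical effect is claimed. A reader might infer that the toxicity pausing rule in Section 15.3.2 is affected. That rule counts events warranting discontinuation under Section 12.3, which names no troponin level, so the documents do not settle whether a patient *excluded* under footnote 7 would count, and any effect cannot be sized.

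**What to change.** Limit the present footnote 7 text to the C1D1 draw before the first study dose, and add: *At all later draws, any troponin elevation requires holding study drugs and cardiac evaluation per Section 12.2.* If the sponsor wants a troponin level that ends treatment, it should be stated in Section 12.3. The cost is footnote wording, with no added scheduled tests.

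Optional and separate: state in footnote 2 that the 48-hour troponin window is before the infusion. Footnote 5 of the same calendar already gives the direction for its 72-hour window.

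Not part of this edit: Section 7.6 re-applies criterion 11 and the Section 7.1 screening to patients starting a second treatment, and its exceptions do not include troponin. Whether the Section 12.2 rule should also govern that re-screening is for the sponsor to decide. It would need changes to Sections 7.1 and 7.6 and could add cardiac evaluations.
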